1.5 Study Rationale

The aim of this observational post market study is to compile real world outcome data on the use of the CE marked MANTA Vascular Closure Device following percutaneous cardiac or peripheral procedures for large bore (10-18F ID) interventional devices. This study also fulfills EU regulatory requirements for post-market clinical follow-up.

1.6 Device Description

1.6.1 Study Materials

The 18F MANTA VCD consists of the closure implant, an 18F insertion sheath, an 18F introducer, and an 8F puncture locating dilator. Similarly, the 14F MANTA VCD consists of the closure implant, a 14F insertion sheath, a 14F introducer and an 8F puncture locating dilator. The MANTA implants are composed of a delivery handle containing an absorbable collagen pad, a stainless steel locking component, and an absorbable polymer toggle that are connected by a non-absorbable suture. Hemostasis is achieved primarily by the mechanical means of the toggle-arteriotomy-collagen sandwich, which is supplemented by the coagulation-inducing properties of the collagen. The extra-vascular stainless steel lock secures and marks the location of the absorbable unit. The MANTA VCD components are not made from latex rubber. The device is sterile and intended for single use only.

1.6.2 Indications for Use

The 14F MANTA Vascular Closure Device is indicated for closure of femoral arterial access sites following the use of 10-14F devices or sheaths (maximum OD/profile of 18F), and the 18F MANTA Vascular Closure Device is indicated for closure of femoral arterial access sites following the use of 15-18F devices or sheaths (maximum OD/profile of 25F).

1.8 Regulatory Classification

The MANTA vascular closure device is classified as a Class III device per rules 8 and 17 of Annex IX of the Medical Devices Directive 93/42/EEC.

1.9 Site Selection and Investigator Training

The primary consideration in operator and site selection for the MANTA registry is adequate experience with large-bore interventions and the MANTA VCD, commitment to safety, and consistency in adherence to the clinical protocol. Prior to performing the MANTA procedures for this registry, training materials will be reviewed with each Investigator and clinical coordinator. The study protocol, appropriate subject selection and enrollment will also be reviewed. All Investigators must have personally performed at least 10 MANTA implants and will be certified as successfully trained on the device use with cases that were proctored by a previously trained Investigator or by a company representative (e.g., local distributor).

Prior to performing the MANTA procedures for this registry, training materials will be reviewed with each Investigator and clinical coordinator. The study protocol, appropriate patient selection and enrollment will be reviewed.

Up to seven sites will be asked to participate in the 12M follow-up visit. Sites who will be invited to participate in the 12M subset will be selected based on number of subjects enrolled, study staff support and SOC procedures at site regarding 12-month follow-up post-procedure. The qualification process of site selection for the 12M subset will begin with the highest enrolling site(s). Other factors taken into consideration for site selection are availability of study staff support and standard of care procedures done at the 12-month visit. Sites selected for the 12M follow-up visit will be considered from all actively participating sites who enrolled subjects .

2. Justification of the Design of the Registry Study

The First in Human study in Paraguay and the EU Pre-Market Clinical Study in the Netherlands and Italy demonstrated that the MANTA VCD is safe and has excellent performance in achieving hemostasis. Due to the favorable feasibility and safety results of these studies, the MANTA VCD was CE marked in 2016. Over 1,000 MANTA large bore vascular closure devices have been successfully deployed globally; however, there has been limited data collection on the performance of the device under real world conditions.

3. Risks and Benefits of the Device and Registry Study

3.1. Anticipated Clinical Benefits

For subjects undergoing procedures requiring large bore sheaths (10-18 F), the potential benefit is that the MANTA device has been successful at closing these arteriotomies without additional complications compared to the suture-mediated closure devices. The method is simple and easy to use and it reduces complications compared to surgical repair.

3.2. *Anticipated Adverse Device Effects*

Use of the MANTA device carries risk from procedural error, inherent use hazards, and device failure. A complete list of anticipated adverse device effects can be found in Section 9.2 - Anticipated Adverse Events and Adverse Device Effects.

Risks from the registry itself are negligible. All of the registry study procedures are standard of care for interventional peripheral and cardiac procedures.

3.3. *Risk Mitigation*

In accordance with ISO 14971:2012, Essential Medical, Inc. has taken measures to ensure the device is designed, manufactured and tested appropriately to mitigate and control these risks through systematic risk analysis, in-process controls and final inspection, labeling, instructions for use, and post-market surveillance. As a result, the residual risk is as low as possible.

3.4. *Risk to Benefit Rationale*

The potential benefits of the MANTA device are expected to outweigh the aforementioned mitigated risks and exceed or meet the performance of current treatment methods, and the study itself carries no additional risk. Therefore, the registry is justified by the risk/benefit ratio.

4. Protocol Definitions

Adjunctive Compression: Compression methods (including sand bags, compression bandages, and light manual pressure) for controlling cutaneous or subcutaneous oozing.

Adverse Device Effect (ADE): Adverse event (see definition below) resulting from insufficient or inadequate instructions for use, deployment, implantation, installation, or operation, or any malfunction of the investigational medical device. This definition includes any event resulting from use error or from intentional misuse of the investigational medical device.

Adverse Event (AE): Any untoward medical occurrence, unintended disease or injury, or untoward clinical signs (including abnormal laboratory findings) in subjects, users or other persons, whether or not related to the medical device. For the purpose of this protocol, AEs to be recorded include AEs associated with the MANTA device, AEs related to the non-MANTA access site, and additional outcomes either associated or not associated with the MANTA device. This definition includes events related to the procedures involved. For users or other persons, this definition is restricted to events related to devices. For the subjects followed up at 12M, only AEs related to the MANTA access site or the ipsilateral leg will be collected.

Cachexia: Defined as very thin, or body mass index $<20 \text{ kg/m}^2$.

Device Deficiency: Inadequacy of a medical device with respect to its identity, quality, durability, reliability, safety or performance; includes device malfunctions, use errors and inadequate labeling

Ecchymosis: An area of subcutaneous discoloration caused by the extravasation of blood into the subcutaneous tissue not associated with a definable, palpable subcutaneous mass.

Hematoma: An expanding or non-expanding subcutaneous mass of blood greater than 2 cm in its longest axis, confirmed by ultrasound.

Hemostasis Success: Hemostasis at the puncture site within 10 minutes of removing the MANTA sheath without need for manual or mechanical compression and without later re-bleeding (trivial or subcutaneous oozing will not be considered bleeding; light finger pressure to control subcutaneous oozing will not be considered manual compression).

Major and Minor Access Site Related Complications (as described below): within 30 days of procedure. Adapted from the VARC-2 Clinical Guidelines [3]

Major femoral vascular complications: Composite endpoint that includes any of the following adverse events:

- Femoral access site or access-related vascular injury (dissection, stenosis, perforation, rupture, arterio-venous fistula, pseudoaneurysm, hematoma, irreversible nerve injury, compartment syndrome, percutaneous closure device failure) leading to death, life-threatening or major bleeding; OR,
- Downstream distal embolization (lower extremities) requiring surgery or resulting in amputation; OR,
- The use of unplanned endovascular or surgical intervention associated with death, major femoral bleeding; OR,
- Any new ipsilateral lower extremity ischemia documented by patient symptoms, physical exam, and/or decreased or absent blood flow on lower extremity angiogram; OR,
- Surgery for femoral access site-related nerve injury; OR,
- Permanent femoral access site-related nerve injury (lasting >30 days).

Minor femoral vascular complications: Composite endpoint that includes any of the following adverse events:

- Femoral access site or access-related vascular injury (dissection, stenosis, perforation, rupture, arterio-venous fistula, pseudoaneurysms, hematomas, percutaneous closure device failure) not leading to death, life-threatening or major bleeding; OR,
- Downstream distal embolization (lower extremities) treated with embolectomy and/or thrombectomy and not resulting in amputation; OR,
- Any unplanned endovascular stenting or unplanned surgical intervention not meeting the criteria for a major vascular complication; OR,
- Vascular repair or the need for vascular repair (via surgery, ultrasound-guided compression, transcatheter embolization, or stent-graft); OR,
- Percutaneous closure device failure*; OR,
- Any other adverse event that is definitely or probably device-related or access-site related.

*Failure of a closure device to achieve hemostasis at the arteriotomy site leading to alternative treatment (other than manual compression or adjunctive endovascular ballooning)

Morbid Obesity: Defined by the position of the access needle whereby less than one third of the access needle is above the skin line indicating the subject is morbidly obese, or body mass index >40 (weight in kg divided by square of height in meters).

Nerve Injury: Any ipsilateral transient or permanent sensory or motor neurologic deficit of the femoral nerve, or anterior or lateral cutaneous femoral nerve, or evidence of sacral plexus injury from documented retroperitoneal bleeding, as determined by a neurologist.

Oozing: Bleeding of a cutaneous or subcutaneous origin that can be controlled with the application of light compression methods (sand bags, compression bandages, or light manual pressure) and which do not apply sufficient compression to control arterial bleeding. Light manual compression may be substituted by light compression from a mechanical device.

Pre-existing Hematoma: An expanding or non-expanding subcutaneous mass of blood present prior to the start of the access site closure.

Serious Adverse Device Effect (SADE): An Adverse Device Effect that has resulted in any of the consequences characteristic of a Serious Adverse Event.

Serious Adverse Event (SAE): An SAE is an Adverse Event that:

- Lead to death
- Lead to life threatening or major bleeding - requiring transfusion of two or more whole blood/RBC
- Lead to a permanent injury or permanent impairment to a body structure or a body function
- In patient or prolonged hospitalization
- Medical or surgical intervention to prevent life-threatening illness
- Lead to visceral ischemia

Note: For this study, planned hospitalization for a pre-existing condition, or a procedure required by this protocol, without serious deterioration in health, is not considered a serious adverse event.

Severe Peripheral Vascular Disease: Any of the following:

- Severe claudication when ambulating <30 meters
- Weak or absent pulses in the affected limb
- Known stenosis >50% in the iliac or femoral artery on the affected side
- Prior vascular bypass surgery involving the affected femoral artery

Significant Calcium: Visible calcium on fluoroscopy or CTA.

Document calcium on MFACS scale (MFACS is not exclusionary)

- Manta Femoral Artery Calcification Score (MFACS)
 - 0 - No calcification
 - 1 - Minor calcification
 - 2 - Moderate anterior and posterior wall calcification
 - 3 - Significant posterior wall calcification
 - 4 - Significant anterior wall calcification
 - 5 - Circumferential wall calcification

Stable Access Site Status: Defined as ability to walk at least 6 meters, freedom from orthostatic hypotension [defined as stable blood pressure and heart rate after ambulating], ability to void and a stable access site without bleeding or expansion of a prior hematoma.

Time to Ambulation: The elapsed time between post-MANTA deployment (time suture cut away from body) and when ambulation is achieved (patient standing and walking at least 6 meters without re-bleeding).

Time to Hemostasis: The elapsed time between MANTA deployment (withdrawal of sheath from artery) and first observed and confirmed arterial hemostasis (no or minimal subcutaneous oozing and the absence of expanding or developing hematoma).

Total MANTA Procedure Time: The elapsed time between pre-MANTA deployment (exchange of procedure sheath with MANTA sheath) to post-MANTA deployment (time suture cut away from body).

Procedure Success: A patient will be considered a Procedure Success if he/she has no Major Complications (as defined above).

Unanticipated Serious Adverse Device Effect (USADE): A Serious Adverse Device Effect, which by its nature, incidence, severity or outcome has not been identified in the current version of the risk analysis report. Note: An anticipated serious adverse device effect is a serious adverse device effect which by its nature, incidence, severity or outcome has been identified in the risk analysis report.

5. Study Objectives

The following Performance Endpoints will be evaluated for the MANTA device (definitions are provided in Section 4):

1. Time to Hemostasis (Primary)

The following Safety Endpoints will be evaluated for the MANTA device (definitions are provided in Section):

1. The percentage of patients with one or more VARC-2 Major femoral vascular complications within 30±7 days following procedure (Primary)
2. The percentage of patients with one or more VARC-2 Minor femoral vascular complications within 30±7 days following procedure (Secondary)

6. Study Design

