9.4. Severity of Adverse Events

The following categories will be used to describe the severity of an AE:

- Mild: awareness of a sign or symptom that does not interfere with the patient’s usual activity or is transient, resolved without treatment and with no sequelae
- Moderate: interferes with the patient’s usual activity and/or requires symptomatic treatment
- Severe: symptom(s) causing discomfort and requires transfusion of 2 or more units of whole blood/RBC

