9.5. Reporting of Adverse Events

9.5.1 SAE and AE Reporting to Sponsor

Safety Surveillance within this registry and the safety reporting performed by both the investigator and Sponsor starts from the point of attempted MANTA placement and onward. The safety surveillance and the safety reporting will continue until the last visit has been performed, the subject is deceased. The subject/investigator concludes their participation in the study or the subject/investigator withdraws the subject from the study. All device-related SAEs from the point of attempted MANTA placement and onward will be reported to the Sponsor within 24 hours of the Investigator’s first knowledge of the event. Suspected SAEs also should be reported. Investigators should also report AEs or SAEs that are known to be unrelated to the device on eCRF.

The Investigator will forward information about a device-related SAE promptly and complete the AE and SAE report forms provided by the Sponsor, even if the information is incomplete or it is obvious that more data will be needed to form any conclusions. Additional information regarding the SAE will be recorded on the follow-up SAE form and forwarded to the Sponsor.

All MANTA device-related AEs, and AE’s associated with non-MANTA access sites, and additional outcomes not associated with MANTA device should be reported on the eCRF as soon as practicably possible. Such AEs will be recorded by their final medical diagnosis and not by each separate symptom. All AEs categorized by the Investigator as associated with MANTA leg and categorized by the Investigator as possibly, probably or definitely device-related, will be reviewed by the Clinical Events Committee for a final adjudication. The information for the event will include the date of onset and resolution, the action taken, the intervention/treatment and how the subject recovered with or without sequelae. In case of death, the relationship of death to the MANTA device and/or the study procedure will be well documented. The date on

which subject expired, what attempts were made to treat the event that led to death, the performance and functioning of the device during the event will be noted.

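### Severe cannot be graded without a transfusion of 2 or more units, and a narrow subset of Major complications, chiefly limb ischemia that resolves early, can fall outside the SAE list and the 24-hour deadline of Protocol 9.5.1

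*Protocol*

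**What the plan says.** **Major complication.** Among the elements of the Major femoral vascular complication in Protocol Section 4 is "Any new ipsilateral lower extremity ischemia documented by patient symptoms, physical exam, and/or decreased or absent blood flow on lower extremity angiogram". It carries no threshold for duration, treatment or hospital stay. The percentage of patients with a Major complication is the primary safety endpoint (Protocol Section 5).

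**Serious.** Protocol Section 4 lists six SAE criteria, repeated in SAP Appendix 1:
- death
- "Lead to life threatening or major bleeding - requiring transfusion of two or more whole blood/RBC"
- lasting harm to the body's structure or function
- admission to hospital or a longer stay there
- intervention to avert a life-threatening illness
- "Lead to visceral ischemia"

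SADE is defined through SAE, and USADE through SADE.

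**Severe.** Protocol 9.4 has three grades. Mild and Moderate rest on interference with usual activity and need for treatment. Severe is "symptom(s) causing discomfort and requires transfusion of 2 or more units of whole blood/RBC".

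**Reporting.** Protocol 9.5.1: "All device-related SAEs from the point of attempted MANTA placement and onward will be reported to the Sponsor within 24 hours". It adds that suspected SAEs should be reported, without a time limit, and sets no fixed deadline for other device-related AEs. Protocol 15.3 gives, among possible reasons for termination, failure to report safety events within 24 hours, as an item separate from failure to report serious adverse device effects.

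**Use in the analysis.** SAP 5.6 shows VARC-2 Major complications and device-related serious AEs as separate overview lines, tabulates SAEs, and lists severity and seriousness for each MANTA-related event.

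**The concern.** Three labels attach to the same event: Major, serious and severe. They come from definitions that were not aligned. The top severity grade depends wholly on transfusion, although several Major elements (ischemia, embolization, nerve injury) need involve no bleeding. The SAE list names ischemia of the viscera but not of the leg, and it recognizes an intervention only when life is threatened.

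The event is foreseeable. Protocol 9.2 lists ischemia from a collagen plug lying inside the femoral artery as a potential device effect. Cohort 1 must also have femoral angiography after closure to check patency, and reduced flow on an angiogram is one way of documenting the ischemia element. The registry therefore looks for this event at a moment when it may be dealt with in the same session, which is when the SAE criteria are least likely to be met.

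At stake are the serious-event summaries, the severity listing and the speed at which the sponsor hears of an event. The seriousness label also matters for device deficiencies: Protocol 9.6 gives 24 hours or 3 business days according to whether a SADE could have resulted.

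**Working it through.** The plan has no figure to reproduce: no hypothesis is tested and the sample size has no statistical basis (Protocol 8.1 and 8.2). The check sets the definitions side by side.

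**Step 1. Count of criteria.** Of the six SAE criteria, bleeding is named in 1, ischemia in 1 (visceral only) and limb ischemia in 0. Of the three severity grades, 1 (Severe) requires transfusion, and no other route leads to it.

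**Step 2. Each Major element against the SAE list and the Severe grade.**

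| Major element | SAE? | Severe without transfusion of 2 or more units? |
|---|---|---|
| Vascular injury or unplanned intervention with death | Yes (death) | No |
| Vascular injury or unplanned intervention with major bleeding | Yes, if major bleeding carries the transfusion condition of the SAE list | No |
| Distal embolization with amputation | Yes (permanent injury) | No |
| Distal embolization requiring surgery | Only with hospitalization or a longer stay, permanent damage, or a threat to life | No |
| New ipsilateral limb ischemia | Only on the same conditions | No |
| Surgery for nerve injury | Only on the same conditions | No |
| Permanent nerve injury | Yes (permanent impairment) | No |

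**Step 3. Two cases of limb ischemia.**
- *Case A:* resolves or is treated within the index stay, with no longer stay, permanent damage, death or transfusion. Major: yes. SAE: no, on a literal reading. Severity: at most Moderate. 24-hour deadline under 9.5.1: none.
- *Case B:* prolongs the stay, leads to readmission or leaves permanent damage. Major: yes. SAE: yes. 24-hour deadline: yes, if device-related. Severity: still at most Moderate unless 2 or more units are transfused.

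The severity gap therefore covers every event without transfusion. The seriousness gap covers only Case A and its counterparts for surgically treated embolization and nerve injury.

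**Step 4. Reporting.** Section 9.5.1 ties the 24-hour limit to device-related SAEs. Section 15.3 implies the limit for safety events generally and names serious adverse device effects separately, so its first item cannot simply mean the second. Case A has no fixed deadline under one section and a 24-hour deadline under the other.

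**Step 5. Primary endpoint.** Under Protocol 9.7 and SAP Section 3, the CEC reviews AEs judged possibly, probably or definitely device-related. Seriousness and severity are not conditions. The SAP's list of events withheld from adjudication covers small or unmeasured hematomas and minor bleeding, not ischemia. A Case A event judged device-related is still adjudicated and can count as Major.

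**Step 6. Size.** The documents give no rate of limb ischemia. One reclassified subject moves the device-related serious AE percentage by 1/500 = 0.2 percentage points at full enrollment. The three Major complications in the EU pre-market study (two bleedings and one pseudoaneurysm) were all SAEs, so they do not test the gap.

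**The case against.** A reader might infer more than the text bears, and the case against those readings is good.

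- *That the whole SAE list is built around bleeding.* Only one of six criteria names it. Death, permanent injury, hospitalization and intervention are general.
- *That every non-bleeding Major escapes the SAE list.* Amputation and permanent nerve injury are caught, as is ischemia that prolongs the stay.
- *That severity is wrong for every non-bleeding event.* Mild and Moderate use functional criteria and grade most such events properly. Only events that would merit the top grade are affected.
- *That these events escape 24-hour reporting altogether.* Section 15.3 points the other way, and Protocol 9.5.1 has all device-related AEs logged as complaints and assessed for vigilance reporting.
- *That the primary endpoint loses events.* It does not, by Step 5.

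All of that stands. Four further arguments stand in part. First, the SAE note excludes planned hospitalization only where health has not seriously deteriorated, so an investigator could argue that acute limb ischemia during the index stay is serious. That makes the classification uncertain rather than settled: two sites could label the same event differently. Second, the CEC is charged with refining SAE definitions, which is a possible remedy, but neither document records a refinement on this point. Third, Major and serious are separate concepts, and the SAP shows them on separate lines; a Major that is not serious is not in itself an error. However, the heading of SAP 5.4 describes long-term Major and Minor complications as SAEs, so the SAP does not keep the two apart consistently. Fourth, severity appears only as a listing column, beside treatment, outcome and the CEC determination, so a careful reader would still see the event.

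**Conclusion.** The point holds in two parts of unequal reach. The Severe rule is a definite defect: no event without transfusion of 2 or more units can be graded above Moderate, whatever its consequence. The seriousness gap is real but narrow: new ipsilateral limb ischemia, or surgically treated embolization or nerve injury, with no prolonged stay, permanent damage or transfusion. Such an event can be Major and non-serious. It has no deadline under Protocol 9.5.1, in conflict with what 15.3 implies.

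The consequences are confined to the SAE, SADE and USADE summaries, the severity listing and reporting speed. The primary endpoint count is not affected, provided the CEC follows its device-relatedness criterion; the sentence that words its primary responsibilities around serious events is narrower. For 12-month events, which Protocol 9.7 leaves unadjudicated and SAP 5.6 summarizes by seriousness, the investigator's label stands alone.

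The number of subjects affected cannot be estimated from the documents. The conclusion rests on a literal reading of the SAE criteria. This is a minor point, but it follows directly from the definitions.

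**What to change.** 1. Protocol 9.4: define Severe by functional impact or need for intervention, with transfusion of 2 or more units as one sufficient criterion rather than a required one.
2. Protocol Section 4 and SAP Appendix 1: add any VARC-2 Major femoral vascular complication to the SAE list.
3. Reconcile Protocol 9.5.1 with 15.3 so that the 24-hour duty is stated once, for a defined set of events.
4. SAP 5.6: cross-tabulate CEC-adjudicated Majors by seriousness and severity, and add a line counting device-related events that are serious or CEC-adjudicated Major. Keep the investigator's recorded seriousness as it stands. Overwriting it would be hard to defend, because enrollment had closed when the SAP was drafted (SAP Section 5).

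Cost: item 4 is one table and one line, and it is useful even if nothing else changes. Items 1 to 3 need a protocol amendment with sponsor, investigator, ethics committee and regulatory approval (Protocol 15.1), and item 1 means re-grading some recorded events. The serious-event count may rise slightly.
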